#### 11.3 PAH-SYMPACT

Responses to the PAH-SYMPACT Questionnaire will be listed for all subjects. The listing will include the date of the questionnaire, nominal study visit, all responses for each subject, and the computed domain scores.

Summaries for each question in the PAH-SYMPACT will be provided by TreT dose and overall at Baseline, Week 3, Week 11 of the Optional Extension Phase, and End of Study Visit. Additionally, summaries of each domain score (Cardiopulmonary Symptoms, Cardiovascular Symptoms, Physical Impacts, Cognitive/Emotional Impacts) will be calculated by TreT dose and overall at Baseline, Week 3, Week 11 of the Optional Extension Phase, and End of Study Visit. Changes in domain scores will be assessed by paired t-tests at Week 3.

#### 12 SAFETY ANALYSES

All safety analyses will be performed on the Safety Population (see Section 8).

#### 12.1 EXTENT OF EXPOSURE

All study drug dosing will be listed for all subjects. The listing will include TreT dose (in mcg), date of first dose, and date of last dose. The duration of exposure and TreT dose during the Treatment Phase and during the Optional Extension Phase will be summarized by assigned TreT dose and overall.

For study treatment compliance, the number and percentage of days with at least 1 dose of TreT will be calculated and summarized by TreT dose and overall for both the Treatment Phase and Optional Extension Phase. Additionally, for each subject, compliance will be calculated as (Total number of doses taken divided by total number of doses supposed to be taken) times 100% and summarized by TreT dose and overall for both the Treatment Phase and Optional Extension Phase.

#### 12.2 ADVERSE EVENTS

All AEs will be coded to the appropriate PT and SOC using MedDRA. AEs will be listed by TreT dose including all details recorded on the eCRF plus an indicator of whether the event was treatment emergent. Treatment-emergent AEs are those AEs with an onset date equal to or after the start date of TreT. The AE listings will include the AE verbatim term and its corresponding PT and SOC.

The AE summaries will be limited to include only treatment-emergent AEs and will be prepared for the Treatment Phase and the combined Treatment Phase and Optional Extension Phase. The non-treatment-emergent AEs (the AEs occur after signing the Informed Consent Form but before receiving TreT) will be listed but not included in summary tables.

All summaries will include the number and percentage of subjects experiencing each type of AE and the total number of each type of AE, in order of overall frequency and/or SOC. Serious adverse events (SAEs) and non-serious AEs will also be summarized by SOC and PT.

The total number of AEs and the AE rates will be calculated and summarized for each display, as appropriate. The AE rate will be calculated as the total number of AEs divided by the total patient years of exposure to study drug per TreT dose.

AEs possibly or probably related to study drug will be summarized. An AE summary by severity (mild, moderate, and severe) will also be provided.

Separate listings and summary tables will be provided for all SAEs, AEs leading to the discontinuation of study drug, and all deaths during the study (if data permit). For the listing

of deaths, information for all subjects who die during the study period from Baseline to the end of the study (including 30 days after the last TreT dose) will be included.

To assess possible underreporting of AEs, an additional summary will be created for AEs by time of enrollment: pre- or post-pandemic.

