Treatment Phase: The Treatment Phase consists of 2 study visits to the clinic separated by 3 weeks of treatment with TreT. At Baseline, subjects will receive 1 dose of Tyvaso in the clinic and undergo PK assessments (at the following timepoints: 15 minutes before dose and 5, 10, 15, 30, 45, 90, 120, 180, 240, and 300 minutes after dose), safety assessments, and a 6MWT. No additional dose of Tyvaso will be administered, nor will TreT be started, until after the PK sampling assessment is complete. Following these assessments, subjects will be assigned a corresponding dose of TreT based upon their current stable Tyvaso dose and will receive the first dose of TreT in the clinic. Each subject will receive TreT QID by oral inhalation for 3 weeks. Following 3 weeks of treatment, subjects will return to the clinic and receive 1 dose of TreT in the clinic and undergo PK assessments, safety assessments, and a 6MWT as performed at the Baseline Visit. Questionnaires evaluating patient preference for inhaled treprostinil devices and patient-reported PAH symptoms and impact will also be administered. At each study visit, AEs will be assessed, vital signs will be recorded, and a physical examination, including oropharyngeal examination, will be performed. Following the Week 3 Visit, subjects may choose to participate in the Optional Extension Phase of the

study. If the subject does not elect to participate in the Optional Extension Phase of the study, he/she must discontinue TreT, may resume Tyvaso therapy, and must return to the clinic 2 weeks after TreT discontinuation for an End of Study Visit. Blood samples for an optional evaluation of change in biomarkers (specific targets to be determined) will be collected at the Baseline Visit and Week 3 Visit. An additional blood sample for an optional evaluation of whole genome sequence will be collected at the Baseline Visit.

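### SAP 12.2 draws the treatment-emergent boundary by date in one paragraph and by receipt of TreT in the next, so Day 1 AEs after the in-clinic Tyvaso dose meet both rules

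*SAP*

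**What the plan says.** - **Definition.** SAP 12.2: "Treatment-emergent AEs are those AEs with an onset date equal to or after the start date of TreT". Only dates are compared. The flag appears in the listing: "AEs will be listed by TreT dose including all details recorded on the eCRF plus an indicator" of treatment-emergent status.
- **Exclusion.** The next paragraph limits the AE summaries to treatment-emergent AEs. It describes the non-treatment-emergent ones as "the AEs occur after signing the Informed Consent Form but before receiving TreT" and says that they "will be listed but not included in summary tables".
- **Rate.** SAP 12.2 computes it as "total number of AEs divided by the total patient years of exposure to study drug per TreT dose".
- **Order of events on Day 1.** SAP 3 has one Tyvaso dose in clinic, PK samples up to 300 minutes, and then the first TreT dose at the same visit: "No additional dose of Tyvaso will be administered, nor will TreT be started, until after the PK sampling assessment is complete". Protocol 7.2 puts the first TreT dose last in its list of Baseline activities.
- **AE collection.** Protocol 3.3.2.6 records AEs from the signing of consent. Protocol 7.3 allows a combined Screening/Baseline Visit, so consent, Tyvaso and first TreT can share one date. Protocol 9.2 calls for AE onset times as well as dates in the eCRF.

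**The concern.** The two paragraphs set different boundaries for the same class of events. In many trials the gap between the start of the first dosing day and the first dose is short and idle, and a date rule does little harm. Here the gap begins with an active inhaled dose of the same molecule by another device. The protocol's hypothesis (Protocol 1.4) includes similar tolerability of TreT and Tyvaso.

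Safety and tolerability of TreT is the primary objective, and the summary tables contain treatment-emergent AEs only. Under the date rule, an AE that began after Tyvaso and before any TreT is tabulated as a TreT event. Under the other rule it is not. Two programmers could follow the section faithfully and produce different tables.

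**Working it through.** **Step 1. Apply both rules to one event.** The clock times are illustrative: Tyvaso at 09:00, last PK sample at 14:00 (300 minutes later), first TreT dose at 14:05, AE onset at 10:00, all on Day 1.

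| Rule in SAP 12.2 | Comparison | Result |
|---|---|---|
| Onset date on or after TreT start date | Day 1 ≥ Day 1: true | Treatment-emergent, in the tables |
| After consent, before TreT received | 10:00 < 14:05: true | Not treatment-emergent, out of the tables |

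The same AE satisfies both.

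**Step 2. Length of the overlap.** The last sample is due at 300 ± 3 minutes (Protocol Table 3-2), so 297 to 303 minutes, or 4.95 to 5.05 hours from the Tyvaso dose. The date rule also takes in AEs earlier on that date. At a combined visit the overlap reaches back to consent. If consent and first TreT share a date, the date rule leaves no post-consent AE in the excluded class.

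**Step 3. Look for a tie-break.** Protocol 10.3.2 does not define treatment-emergent. SAP Table 9-2 slots visit assessments and does not cover AEs. Protocol 15.2 places events that precede study drug under not related. That partly protects the related-AE table but does not decide treatment-emergence.

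**Step 4. Weight of one misplaced event.** The plan gives no figure to reproduce. The inputs are 45 planned subjects (SAP 7), 3 weeks of treatment (SAP 3) and a Week 3 window of ± 3 days (Protocol Table 3-1, footnote c). The added rate per AE is 1 / (n × days / 365.25).

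- 21 days: 45 × 21 / 365.25 = 2.587 patient-years; 1 / 2.587 = 0.39 per patient-year.
- 24 days: 2.957 patient-years; 0.34.
- 18 days: 2.218 patient-years; 0.45.
- One affected subject: 1 / 45 = 2.2%.

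Dose-group sizes are not in the documents. For assumed groups of 5, 15 and 30 at 21 days, the exposure is 0.287, 0.862 and 1.725 patient-years, and one AE adds 3.48, 1.16 and 0.58 per patient-year.

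The combined Treatment and Extension tables dilute the effect. As an illustration only, if all 45 were followed on TreT to Week 11 (77 days), 45 × 77 / 365.25 = 9.487 patient-years and one AE adds 0.11.

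**Step 5. How many events.** The documents do not give the chance p that a subject has an AE in the window. Under assumed values, with subjects independent, the expected number affected is 45p and P(at least one) = 1 − (1 − p)^45.

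| Assumed p | Expected subjects | P(at least one) |
|---|---|---|
| 1% | 0.45 | 0.36 |
| 2% | 0.9 | 0.60 |
| 5% | 2.25 | 0.90 |
| 10% | 4.5 | 0.99 |
| 20% | 9 | about 1.00 |

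**The case against.** The strongest reply is that SAP 12.2 has one operative definition, the date rule, and that the later parenthesis only describes its complement loosely. Rewording the parenthesis to refer to the TreT start date would then remove the contradiction. That is a fair reading, and it would make the text consistent. It would still count Tyvaso-window AEs as TreT AEs, although the SAP says that events before TreT stay out of the tables and onset times are to be collected.

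Four further points stand and limit the size:

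- The date rule can only add events to TreT. It cannot lose a true TreT event, so it errs on the cautious side for safety.
- The study is uncontrolled, descriptive and not powered, and no decision rests on these rates.
- Protocol 9.1.1 does not count day-to-day fluctuations of existing conditions that do not worsen as AEs, and the listing lets a reader trace single events.
- The Safety Population needs at least one TreT dose (SAP 8). An SAE in the Tyvaso window reaches the SAE table only if the subject still goes on to TreT.

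The 0.39 figure is also simply the weight of any single AE in 2.59 patient-years. It shows how much one event matters, not how often the error occurs.

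**Conclusion.** The inconsistency is real and affects Day 1 for every subject, but its consequence is minor. As written, the date rule places AEs from the 5 hours or so after Tyvaso in the TreT all-AE, severity and rate tables, and in the SAE table only for subjects who are then dosed with TreT. Each such AE is worth about 0.39 per patient-year overall in the Treatment Phase (0.34 to 0.45 across the visit window), more within a dose group and less in the combined-phase tables. These figures assume 45 treated subjects who all complete. The number of such AEs is unknown.

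Two stronger readings are tempting, and the documents do not support them.

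- A reader might infer that the TreT safety profile is materially inflated, pointing to the cough (54%), headache (41%) and nausea (19%) in the Phase 3 trial of inhaled treprostinil (Protocol 1.2.3.1). Those rates come from 12 weeks in subjects newly allocated to the drug. Here subjects have been on Tyvaso for at least 3 months on a stable dose, and the window is about 5 hours.
- A reader might infer that, because the definition has no end date, AEs after TreT is stopped are also miscounted or lost. Without an end date those AEs stay treatment-emergent, and SAP 9.3 uses all available Safety Population data. The assignment of that period to a phase is not spelled out, but the documents show neither the size nor the direction of any effect.

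**What to change.** In SAP 12.2, define a treatment-emergent AE as one with onset date and time at or after the date and time of the first TreT dose. Treat Day 1 AEs with a missing onset time as treatment-emergent. Word the description of non-treatment-emergent AEs to the same boundary, and keep those events in the listing with the indicator set accordingly.

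The sponsor should confirm that the clock time of the first TreT dose is recorded, because SAP 12.1 lists only dates of first and last dose. If it is not, use the time of the last Baseline PK sample as the boundary, but only where that sample was taken and no deviation shows that TreT was given earlier. In all other cases treat Day 1 AEs as treatment-emergent, so that the fallback cannot drop a true TreT event.

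The cost is a few sentences in the SAP and minor programming. AE onset times are already to be collected (Protocol 9.2), and PK sampling times are already listed (SAP 13). No study procedure changes, apart from a possible added field if the sponsor chooses to capture the first-dose time.

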9.1.1 Adverse Event

An AE is any untoward medical experience occurring to a subject during the clinical study whether or not it is related to the study drug.

An AE may include any of the following:

- An intercurrent illness, injury, or any other concomitant impairment of the subject's health, as well as abnormal laboratory findings if deemed to have clinical significance.
- A worsening of existing symptom or condition or post-treatment events that occur as a result of protocol-mandated procedures (eg, exacerbation of a pre-existing illness following the start of the study or an increase in frequency or intensity of a pre-existing episodic event or condition).

Thus, no causal relationship with the study drug is implied by the use of the term "adverse event."

An AE does not include the following:

- Medical or surgical procedures (eg, surgery, endoscopy, tooth extraction, transfusion); however, the condition for which the surgery is required may be an AE.
- Planned surgical measures permitted by the study protocol and the condition(s) leading to these measures are not AEs.
- Day-to-day fluctuations of pre-existing disease or conditions present or detected at the start of the study that do not worsen.
- Situations where an untoward medical occurrence has not occurred (eg, hospitalizations for cosmetic elective surgery, social and/or convenience admissions).

All AEs will be documented from the time of informed consent until the time screen failure is documented, or until the subject is either discontinued from the study or all End of Study Visit assessments have been completed.

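### SAP 12.2 gives treatment-emergent AEs a start but no end, so AEs after TreT is stopped either inflate a rate based on TreT exposure or drop out of every summary

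*SAP*

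**What the plan says.** SAP Section 12.2 classifies AEs by onset date: "Treatment-emergent AEs are those AEs with an onset date equal to or after the start date of TreT". The only other class is described as follows: "non-treatment-emergent AEs (the AEs occur after signing the Informed Consent Form but before receiving TreT) will be listed but not included in summary tables". No post-TreT class is defined.

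The same section sets the rate for each dose level: "AE rate will be calculated as the total number of AEs divided by the total patient years of exposure to study drug". It says that AE summaries "will be prepared for the Treatment Phase and the combined Treatment Phase and Optional Extension Phase". SAP Section 12.1 records exposure by dose dates: "The listing will include TreT dose (in mcg), date of first dose, and date of last dose".

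For a subject who does not enter the extension, SAP Section 3 says "he/she must discontinue TreT, may resume Tyvaso therapy, and must return to the clinic 2 weeks after TreT discontinuation". Protocol Section 9.1.1 keeps AE collection open "until the subject is either discontinued from the study or all End of Study Visit assessments have been completed". The schedule of events in Protocol Section 3.2 allows ±3 days for the Week 3 and End of Study Visits.

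Within SAP 12.2, the only limit after dosing is the 30 days after the last TreT dose that applies to the listing of deaths.

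**The concern.** The primary objective is the safety and tolerability of TreT, so the AE tables and rates by TreT dose are its main evidence. For a subject who declines the extension, AE collection outlasts TreT by about 2 weeks. During that time the subject may be back on Tyvaso, which contains the same active drug. In the background sections of the protocol, cough and headache are the leading AEs for both products, so the preferred term alone will not show which product a subject was taking.

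The treatment-emergent definition takes in these AEs, while study-drug exposure ends at the last TreT dose. Any such AE that enters a rate display adds to the numerator and nothing to the denominator. If instead the phase labels are meant to keep the follow-up out, the SAP gives these treatment-emergent AEs no place in any summary table. The SAP does not choose between the two.

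**Working it through.** The documents state no AE rate, event count or share of decliners, so there is no planned figure to reproduce. The check first sets the text side by side and then sizes the effect.

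**Text**

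1. The treatment-emergent class begins at the TreT start date. The non-treatment-emergent class is confined to the time before TreT. Together they cover all AEs, so an AE that begins after the last TreT dose is treatment-emergent.
2. Summaries are by phase, but no dates assign an AE to a phase. SAP Table 9-2 sets analysis windows for ECG, the two questionnaires, laboratory tests, vital signs and 6MWT. It sets none for AEs.
3. Reading A: follow-up AEs are counted in the Treatment Phase or the combined display. Numerator and denominator then cover different time.
4. Reading B: follow-up belongs to neither phase. These AEs are then treatment-emergent but in no summary table.

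**Size under Reading A**

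Inputs from the documents: 21 days on TreT (3 weeks, ±3 days), 14 days off TreT (2 weeks, ±3 days), and N = 45. Assumptions: a constant AE hazard, and a share s of subjects who decline.

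*One decliner:* ratio of the computed rate to the on-TreT rate = (on + off)/on.
- (21 + 14)/21 = 35/21 = 1.67.
- With 11 to 17 days off: 32/21 = 1.52 to 38/21 = 1.81.
- With on-TreT time of 18 to 24 days as well: 35/24 = 1.46 to 35/18 = 1.94.

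*Treatment Phase display:* ratio = (45×21 + 45×s×14)/(45×21) = 1 + s×14/21.

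| Share declining (assumed) | Same hazard after TreT | Half the hazard after TreT |
|---|---|---|
| 0% | 1.00 | 1.00 |
| 5% | 1.03 | 1.02 |
| 10% | 1.07 | 1.03 |
| 20% | 1.13 | 1.07 |
| 50% | 1.33 | 1.17 |
| 100% | 1.67 | 1.33 |

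*Combined display:* let continuers have a mean total of T weeks on TreT (assumed). Mean exposure per subject is D = (1 − s)×7T + 21s days, and the ratio is (D + 14s)/D. At s = 20%:
- T = 11: D = 65.8, so 68.6/65.8 = 1.04.
- T = 27: D = 155.4, so 158.2/155.4 = 1.02.
- T = 51: D = 289.8, so 292.6/289.8 = 1.01.

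If the numerator and denominator cover the same interval, the ratio is 1.00 in every case.

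**The case against.** The strongest reply is that the phase labels already exclude the follow-up. SAP Section 3 describes the Treatment Phase as two visits separated by 3 weeks of TreT. Decliners stop at the end of that phase, Protocol Table 3-1 gives the End of Study Visit its own column outside both phases, and decliners never enter the extension. This is a fair reading. A reader might infer that every follow-up AE is certain to be tabulated under a TreT dose, and the documents do not support that. But no rule for assigning AEs to phases is written down, and Reading B has its own cost: it leaves treatment-emergent AEs out of all summaries. SAP Section 9.3 says that all available data from the Safety Population will be used as the plan details.

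Other points stand in part:

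- The size is uncertain. The decline share is not documented, and subjects had used Tyvaso for at least 3 months at a stable recent dose, so new AEs on resuming it may be fewer. Protocol Section 7.5 puts the End of Study Visit within 2 weeks, so the off-TreT period may be shorter. Tyvaso is optional, so some of these AEs occur off both products.
- Early termination visits are due as soon as possible, so subjects who stop early add little time after TreT.
- The summary of related AEs, the AE listing and the listed last-dose dates allow partial separation. They do not change the overall incidence and rate displays.
- Counting late events is conservative and hides nothing. That supports keeping an all-AE table, but not a rate with mismatched time.
- The study is descriptive and unpowered, and no test or decision rule uses the AE rate. This limits the consequence.

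**Conclusion.** The gap is real and worth closing. SAP 12.2 has no end to treatment emergence, a rate denominator limited to study-drug exposure, and no statement of where AEs from the 2-week follow-up belong. Neither available reading gives a sound result.

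The direction under Reading A needs no hazard assumption: counted follow-up AEs can only raise the rate. The size does need assumptions. At a constant hazard the factor is 1.67 for one decliner. The Treatment Phase rate for 45 subjects is about 1.07 or 1.13 times its on-TreT value if 10% or 20% decline, and nearer 1 if the hazard after TreT is lower. In the combined display the factor is about 1.04 or less at 20% or fewer declining, for assumed mean TreT durations of 11 to 51 weeks in continuers. If everyone continues, or if Reading B is intended, the rate is not inflated.

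A reader might also infer that the distortion differs between dose groups, because subjects who dislike TreT may decline more often. The documents give no decline shares by dose, so any such imbalance is undocumented.

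**What to change.** In SAP Section 12.2:

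1. Define the on-TreT AE period as the first through the last TreT dose. If a fixed lag is added, state its length and add the same days to the denominator.
2. Use only AEs with onset in that period in the rate numerator.
3. Tabulate AEs with later onset separately as post-TreT, and flag in the listing whether Tyvaso had been resumed at onset.
4. State which display holds the follow-up AEs of subjects who decline the extension.
5. Keep the all-AE incidence table.

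The cost is SAP wording, one derived flag and one extra table. The last TreT dose date and medication start dates are already planned for listing (SAP Sections 10.1, 10.3.3 and 12.1), so no new data or visits are needed. The downside is that a delayed TreT effect would appear in the post-TreT and all-AE tables rather than in the rate.

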15.2 GUIDELINES AND DEFINITIONS FOR RECORDING ADVERSE EVENTS

The Investigator or a designated member of his/her staff will probe each subject for any AEs that may have occurred. The Investigator should always ask the same question when conducting the verbal probe in order to ensure uniformity between subjects. The Investigator should ask:

"How are you doing (feeling)?"

Based on the subject's response to this question, the Investigator should ask additional questions relevant to the specific complaint such as:

"How severe is/was the symptom?"

"How often did the symptom occur?"

"How long did the symptom last?"

It is the Investigator's responsibility to review the results of all diagnostic and laboratory tests as they become available and ascertain if there is a clinically significant change from baseline. If the results are determined to be a clinically significant change from baseline, this should be reported as an AE. The Investigator may repeat the diagnostic procedure or laboratory test or request additional tests to verify the results of the original tests. When possible, a diagnosis associated with the abnormality should be used as the reported AE.

Using provided definitions, the Investigator will then:

(1) rate the intensity and seriousness of the AE, (2) estimate the causality of the AE to study drug, and (3) note actions taken to counteract the AE.

Definitions of Intensity, Seriousness, Causality, Action Taken, and Outcome

INTENSITY

An assessment of the relative intensity (severity) of an AE is based on the Investigator's clinical judgment. The maximum intensity encountered during the evaluation period should be checked. The assessment of intensity should be independent of the assessment of the seriousness of the AE.

SERIOUSNESS

An SAE is one that represents an actual or potential significant hazard. This includes, but is not limited to, an event that is fatal, life-threatening, permanently or severely disabling, requires or prolongs inpatient hospitalization, is a congenital abnormality (offspring of subject), or is medically significant (important medical events that may not result in death, be life-threatening, or require hospitalization may be considered an SAE when, based upon appropriate medical judgment, they may jeopardize the subject and may require medical or surgical intervention to prevent 1 of the outcomes listed in this definition).

Hospitalizations that would not be considered SAEs include those for:

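### The treatment-emergent AE rule uses onset date alone, so an AE that opens in screening and worsens on TreT can miss the summary tables, while a Day 1 event on Tyvaso is counted as a TreT event

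*SAP*

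**What the plan says.** **SAP 12.2** sets the rule: "Treatment-emergent AEs are those AEs with an onset date equal to or after the start date of TreT". It adds that "The AE summaries will be limited to include only treatment-emergent AEs". AEs arising between consent and TreT "will be listed but not included in summary tables". The listings are complete: "AEs will be listed by TreT dose including all details recorded on the eCRF plus an indicator of whether the event was treatment emergent".

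**Protocol 15.2 (Intensity)** tells the site how to grade an AE: "The maximum intensity encountered during the evaluation period should be checked". It describes no dated record of changes in intensity.

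**Protocol 9.1.1** says that an AE may include "A worsening of existing symptom or condition or post-treatment events that occur as a result of protocol-mandated procedures", and gives as one example "an increase in frequency or intensity of a pre-existing episodic event or condition".

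**Timing.** AEs are recorded from consent (Protocol 3.3.2.6). Screening takes place within the 14 days before Baseline (Protocol 3.1). On Day 1 the subject takes Tyvaso in the clinic, has 300 minutes of PK sampling, and only then takes the first TreT dose.

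**The concern.** Safety and tolerability of TreT is the primary objective, and the AE summaries are its main output. Every subject moves from one inhaled treprostinil product to another. Cough and headache were the leading AEs both in the placebo-controlled Tyvaso study and in the healthy-volunteer TreT study (Protocol 1.2.3). A shared symptom that becomes worse after the switch is therefore a plausible form of intolerance to TreT.

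A rule based on onset date alone cannot see such a change if the symptom was already an open AE and the site keeps it as one record. The record carries its pre-TreT onset date and its highest intensity. Because no dated intensity is described, programming could not recover the worsening afterwards. Protocol 15.2 also lists an event that precedes the first dose of study drug under the not-related category, so the same record may be rated unrelated even if TreT aggravated it. With about 15 centres and no instruction in either document, sites could handle the same worsening differently.

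**Working it through.** The plan gives no figure that depends on this definition, and its 45 subjects come from no calculation (Protocol 10.2), so there is nothing to reproduce. The check applies the rule (onset date on or after the TreT start date, Day 1) to the possible record patterns.

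| Pattern | Onset date(s) on record | In AE summaries? |
|---|---|---|
| 1. AE opens Day -7, worsens Day 5, kept as one record | Day -7 | No |
| 2. AE opens Day -7, worsening entered as a new AE on Day 5 | Day -7 and Day 5 | Yes (Day 5 record) |
| 3. AE opens on Day 1 after Tyvaso, before TreT | Day 1 | Yes |
| 4. Symptom predates consent, worsening entered as an AE on Day 5 | Day 5 | Yes |

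Only pattern 1 loses the worsening. The documents do not say whether a site should follow pattern 1 or pattern 2. Protocol 9.1.1 permits pattern 2, and the maximum-intensity instruction in Protocol 15.2 fits pattern 1.

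Pattern 3 is the reverse error. Tyvaso and TreT share a calendar date, so a Tyvaso-period event meets the date rule. Yet SAP 12.2 describes non-treatment-emergent AEs as those after consent and before TreT is received. The two statements disagree for Day 1.

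**Size.** The documents give no rate for pattern 1. Let q be the assumed share of subjects with such an event, and n = 45:

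- expected number affected = n × q
- P(at least one affected) = 1 − (1 − q)^45

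| q (assumed) | Expected subjects | P(at least one) |
|---|---|---|
| 1% | 45 × 0.01 = 0.45 | 0.36 |
| 2% | 45 × 0.02 = 0.90 | 0.60 |
| 5% | 45 × 0.05 = 2.25 | 0.90 |
| 10% | 45 × 0.10 = 4.5 | 0.99 |

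Each subject omitted or restored moves an incidence by 1/45 = 2.2 percentage points. The overall any-AE row moves only if that subject has no other treatment-emergent AE. Otherwise only the preferred-term, system organ class or severity rows move.

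**Severity by phase.** SAP 12.2 plans AE summaries for the Treatment Phase and for the two phases combined. If an AE is mild in the Treatment Phase, becomes severe in the extension and stays one record, its maximum intensity goes into both. The combined table is right. The Treatment Phase table shows a severity that was not reached in that phase.

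**The case against.** The strongest reply is that most of the plausible problem is already handled. Subjects must have started Tyvaso at least 3 months before Baseline, with no dose change in the last 30 days (Protocol 4.1, criterion 6). Established cough, headache or throat irritation will usually predate consent and so is not an open AE. Under Protocol 9.1.1 its worsening is an AE in its own right, with an onset on TreT, and is tabulated. What remains exposed is a symptom that first arises in at most 14 days of screening, is still open at the switch and is kept as one record. With a combined Screening/Baseline visit that window all but disappears. This stands, and it is why the effect is probably small.

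A reader might infer that worsening on TreT is left out of every AE table. The documents do not support that. The restriction applies to summaries. SAP 15.1 includes listings of deaths and of SAEs, and the full AE listing carries a treatment-emergent flag. Discontinuations are also summarised by reason in subject accountability (SAP 10.1), with no AE-onset test.

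A reader might also infer that the bias always favours TreT. It does not: counting Day 1 Tyvaso-onset events, and carrying extension severity back into the Treatment Phase table, both make TreT look worse.

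Finally, eCRF completion guidelines may already tell sites to re-enter a worsened AE. They are not among these documents, so that cannot be confirmed. Such guidance would not settle Day 1.

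**Conclusion.** The gap is real but narrow. As written, SAP 12.2 omits from the AE summaries any AE that begins between consent and the day before TreT, is held as one record, and becomes more intense or serious on TreT. It also counts Day 1 events that began on Tyvaso before TreT was given, against its own description of what is not treatment-emergent.

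The number affected cannot be taken from the documents. An assumed 1% to 10% of subjects gives 0.45 to 4.5 of 45, at 2.2 percentage points each. The short screening window and Protocol 9.1.1 make the lower part of that range more likely. No net direction of bias can be claimed. The point merits a change because the rule governs how the primary objective is summarised and the correction is a matter of wording.

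**What to change.** 1. **SAP 12.2.** Define a treatment-emergent AE as one with onset, or with an increase in intensity or seriousness, after the first TreT dose. On Day 1, compare onset time with the time of that dose. Protocol 9.2 already asks for onset times. State how a missing Day 1 time is handled.
2. **Protocol 15.2 and eCRF completion guidance.** When an AE open at the switch worsens after the first TreT dose, enter a new record with a new onset date. Do the same when an open AE worsens after entry to the extension, so that the Treatment Phase severity table shows the intensity reached in that phase.

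**Cost.** One revised definition, one site instruction and a few more AE records. Total AE counts and the AE rate per patient-year, whose numerator is the number of AEs, would rise slightly. Day 1 events that began on Tyvaso would leave the summaries and stay in the listings. The net effect on reported incidence could go either way.
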